## **8.2. Medical History and Concomitant Diseases**

Medical history information will be coded using Medical Dictionary for Regulatory Activities (MedDRA) version 23.1, summarized and presented overall for the MTX and ITT Populations and by treatment as described in Section 6.1. Summaries will be ordered alphabetically by system organ class (SOC) and then, within a SOC, alphabetically by preferred term (PT).

Medical history data will be listed.

## **8.3. Medication**

Medications will be coded using World Health Organization (WHO) Drug Global B3 September 2018 dictionary. Prior medications, concomitant medications used during the MTX Tolerability Assessment Period, concomitant medications used during the Run-in Period, concomitant medication used in the Pegloticase + IMM Period, and medications used in the Follow-up Period will be summarized by presenting the counts and percentage of subjects using medications overall for the MTX, ITT, and mITT (Follow-up Period only) Populations and treatment as described in Section 6.1. Summaries will be presented by Anatomical Therapeutic Chemical (ATC) Level 4 term and preferred drug name. Medication summaries will be sorted alphabetically by ATC Level 4 and by preferred drug name within ATC Level 4. Subjects will be counted only once for each medication class and each preferred drug name.

Prior and concomitant medications will be listed together with a designation to identify the period(s) of usage and sorted by start date. For determination of period(s) of use, missing date imputation rules are provided in Section 6.3.1.

Any medication with a start date prior to the date of first dose of treatment in the MTX Tolerability Assessment Period will be considered a prior medication.

The following medications will be considered concomitant in the MTX Tolerability Assessment Period

- A medication with a start date on or after the first dose date of MTX in the MTX Tolerability Assessment Period but excluding medications with:
  - Start date on or after the first MTX or placebo date in the Run-in Period and
  - Those started more than 30 days after the last MTX dose, for subjects who did not receive MTX or placebo in the Run-in Period and did not receive an infusion of pegloticase.
- Medications with a partial start date with month and year of start provided and the year of start and month of start match the month and year of first MTX date in the MTX Tolerability Assessment Period and match the month and year of first MTX or placebo date in the Run-in Period will be classified as being used in the MTX Tolerability Assessment Period and in the Run-in Period.

- A medication with a start date prior to the first dose date of MTX in the MTX Tolerability Assessment Period with a stop date strictly after the first dose date of MTX in the MTX Tolerability Assessment Period
- A medication with a start date prior to the first dose date of MTX in the MTX Tolerability Assessment Period that was ongoing.

The following medications will be considered concomitant in the Run-in Period

- A medication with a start date on or after the first dose date of MTX or placebo in the Run-in Period but excluding medications with:
  - Start date on or after the first infusion date of pegloticase and
  - Those started more than 30 days after the last MTX or placebo dose in the Run-in Period, for subjects who did not receive an infusion of pegloticase.
- Medications with a partial start date with month and year of start provided and the year of start and month of start match the month and year of first MTX or placebo date in the Run-in Period and match the month and year of first Pegloticase infusion will be classified as being used in the Run-in Period and in the Pegloticase + IMM Period.
- A medication with a start date prior to the first dose date of MTX or placebo in the Run-in Period with a stop date strictly after the first dose date of MTX or placebo in the Run-in Period
- A medication with a start date prior to the first dose date of MTX or placebo in the Run-in Period that was ongoing.

The following medications will be considered concomitant in the Pegloticase + IMM Period

- A medication with a start date on or after the first infusion date of pegloticase but excluding medications with start date more than 30 days after the date of the end of the last pegloticase infusion.
- A medication with a start date prior to the first infusion date of pegloticase in the Pegloticase + IMM Period with a stop date strictly after the first infusion date of pegloticase in the Pegloticase + IMM Period.
- A medication with a start date prior to the first infusion date of pegloticase in the Pegloticase + IMM Period that was ongoing.
- Medications with a partial start date with month and year of start provided and the year of start and month of start match the month and year of first MTX or placebo date in the Run-in Period and match the month and year of first Pegloticase infusion will be classified as being used in the Run-in Period and in the Pegloticase + IMM Period.

The following medications will be considered concomitant during the Follow-up Period

- A medication with start date prior to 30 days after last dose of study medication that continued use or had a stop date on or after 30 days after the last dose of study medication.
- A medication with a start date more than 30 days after the last dose of study medication.

As such, the same medication may be summarized in one or more of prior, concomitant in the MTX Tolerability Assessment Period, concomitant in the Run-in Period, or concomitant in the Pegloticase + IMM Period. The summary tables will not be mutually exclusive. Missing date imputation rules are provided in Section 6.3.1.

A summary of medications used for gout treatment taken after the last dose of pegloticase will be produced for the mITT Population.

#### 8.3.1. Concomitant Procedures

A listing will be provided for concomitant procedures the subject underwent during the study. No other analysis is planned for concomitant procedures.

## **9. Efficacy**

### **9.1. Handling Rules for sUA Values**

Serum samples for measurement of sUA levels are scheduled for collection at the Screening Visit, the Week -6 Visit (prior to the first dose of MTX), the Week -4 Visit (Randomization) and the Week -2 Visit during the Run-in Period; On Day 1, a pre-dose and post dose sUA will be collected to be shipped to the Central laboratory. For the remainder of study visits beginning at Week 2 during the Pegloticase + IMM period, 2 Serum Uric Acid samples will be collected within 48 hours PRIOR to each pegloticase infusion. One sample will be for testing at the site's local laboratory for sUA levels and the second sample will be sent to the Central Laboratory. A post-infusion sUA blood sample will additionally be collected on Day 1, and at the Weeks 2, 6, 10, 12, 14, 20, 22, 24, 32, 34, 36, 48 and 50 for same day shipment to the Central Laboratory. Additional serum samples for sUA levels are collected at non-infusion Visits at Weeks 21 and 23 and the End of Pegloticase Infusions Visit (if applicable) and the Week 52/End of study/Early Termination Visit and 3 and 6 month Follow-up Visits. Subjects with an sUA level >6 mg/dL at 2 consecutive study visits beginning with the Week 2 Visit will discontinue pegloticase and complete the End of Pegloticase Infusions Visit (if applicable) or the Week 52/End of study/Early Termination Visit procedures.

- For the determination of sUA responder endpoints, scheduled assessments of sUA and unscheduled assessments of sUA, reported by the central laboratory, will be used. Local laboratory-processed pre-infusion sUA results will be used only when the central laboratory-processed value at a time point is not available, but the local lab-processed pre-infusion value, collected value at the same time point, is available.
- When the central laboratory or local laboratory reports a value for sUA as being lower than the lab assay's limit of quantification (e.g. "<0.02"), zero will be used as the numeric value for the purpose of determining response and for summaries of observed values and the change from baseline.

### **9.2. Primary Efficacy Endpoint and Analysis**

This study will compare pegloticase 8 mg co-administered with MTX to pegloticase 8 mg co-administered with placebo in subjects with uncontrolled gout. The primary efficacy endpoint is the proportion of Month 6 (Weeks 20, 21, 22, 23, and 24) responders, defined as subjects achieving and maintaining sUA < 6 mg/dL for at least 80% of the time during Month 6. The objective is to demonstrate superiority of pegloticase given with MTX over pegloticase given with placebo. The primary comparison will be made for ITT population, i.e., all randomized subjects, regardless of adherence to study treatment. The comparison is between randomized (planned) treatment groups of pegloticase given with MTX over pegloticase given with placebo.

[figure not shown]
#### **9.2.1. Calculation of Response**

The sUA concentrations vs. time (collected to the nearest minute in the CRF) curve will be used to estimate the proportion of time that the sUA is < 6 mg/dL using the available pre-infusion (or values at visit when no infusion performed) and post-infusion samples with non-missing sUA values.

The Month 6 period will include pre-infusion and post-infusion results at Week 20, results at Week 21, pre-infusion and post-infusion results at Week 22, results at Week 23, and pre-infusion results at Week 24, and unscheduled assessments of sUA collected between Week 20 and Week 24

This document is confidential.

processed by the central laboratory. Results from visits where an infusion was not performed (e.g. subject discontinued pegloticase but remained in study) will be used when available. Section 9.1 shows the rules for inclusion of sUA values reported by local laboratories.

### 9.2.2. Handling of Missing Data and Multiple Imputation Process

At least two sUA observations from different visits during Month 6 must be available in order for a subject to be eligible for consideration as a responder. Subjects with only one sUA observation will be considered non-responders, regardless of the value of that single observation; subjects with no sUA values will also be considered non-responders. In addition, subjects who meet the stopping rule (sUA values > 6 mg/dL at 2 consecutive scheduled visits (excluding post-infusion sUA) starting at Week 2 prior to or during Month 6 will be considered to be non-responders. For determination of stopping rule, as specified in Section 9.1, if both central lab and local lab sUA results are available at a visit then the central lab value will be used for stopping rule determination. For subjects with missing data due to COVID-19 that is not “Site Closure”, there will be no imputation of sUA values due to missing values among those collected between Week 20 and Week 24.

For subjects with missing data due to site closure (due to COVID-19 as defined in Section 6.3.3) during Month 6 (i.e. have < 2 visits during Month 6 with sUA available), multiple imputation will be used to impute missing sUA values .

The multiple imputation process for imputing missing sUA will involve the following steps:

- 1) For subjects who met the stopping rule and have missing data prior to or during Month 6, last observation carried forward (LOCF) imputation will be done in order to prevent the

This document is confidential.

multiple imputation algorithm from imputing data inconsistent with known information. For example, subjects who meet the sUA stopping rule and have missing sUA after stopping rule is met would be expected to continue to have sUA > 6 mg/dL in the absence of other treatment, and thus would be expected to be non-responders. LOCF is used to provide complete data for stopping rule subjects that may be used to impute missing sUA for "Site Closure" subjects. Note that these LOCF values will only be used in the imputation model, and will be excluded from all analyses once the imputation model has been used.

- 2) A regression model will be created using observed data (after imputation specified in step #1 performed) from subjects not affected by site closures. A linear regression model will be fit for each sUA value comprising Month 6 (i.e., Week 20, Week 21, Week 22, Week 23, Week 24) as the dependent variable and will include independent variables of treatment group, tophi presence, sex, age, baseline weight, race (white, non-white), available pre-infusion sUA values from Day 1 up through the timepoint of each dependent variable, serious AE (yes or no), severe AE (yes or no), and number of gout flares during the Pegloticase + IMM Period up through Month 6.
- 3) Based on the fitted regression model, a new regression model is simulated from the posterior predictive distribution of the parameters, and the predictive mean matching method is used to impute missing values (Rubin 1987, pp. 166–167, Heitjan and Little 1991; Schenker and Taylor 1996). The predictive mean matching method imputes a value chosen randomly from a set of observed subjects with complete data (K=10) whose predicted values are closest to the predicted value for the missing entry from the simulated regression model. This will be implemented using the MI procedure in SAS with the fully conditional specification (FCS) method. Covariates will be removed from the model if the model is unable to converge due to quasi or complete separation. Missing results for covariates will be imputed using either linear regression (for continuous variables) or logistic regression or discriminant function method (for categorical variables).
- 4) The imputation model will be used to create 100 datasets with random number generation. These 100 datasets will include the data from subjects not impacted by COVID-19 and imputed data from subjects with "Site Closure" missing data, resulting in 100 apparently complete datasets.
- 5) Each subject will be classified as a responder or non-responder in each of the 100 apparently complete datasets, and the proportion of responders will be calculated for each of the 100 datasets. For subjects who meet the "Site Closure" criteria (as specified in Section 6.3.3), the imputed sUA values during Month 6 will be used to classify each subject as a responder or non-responder during Month 6. Since date and time of sUA collections during Month 6 will be missing, a duration of 7 days (168 hours) will be used for time between each visit (i.e. Week 20 to Week 21, etc.). Thus, a total time of 28 days (672 hours) during Month 6 will be used to calculate proportion of time sUA < 6 mg/dL. For all other subjects, the actual data from the study (and no imputed data) will be used to classify each subject as a responder or non-responder during Month 6.

SAS code for this analysis can be found in Appendix 19.1. Since the reason for the missing data is known to be due to the COVID-19 pandemic (documented via protocol deviation), it is reasonable to assume that the missing data is missing at random or missing completely at random (MCAR), and therefore multiple imputation is an appropriate method to use. Predictive mean

This document is confidential.

matching avoids distributional assumptions on the sUA values and avoids imputing values that are out of range (e.g., values less than 0, which cannot occur). Using multiple imputation when data are MCAR is more efficient than analyzing observed data only, due to the increased information, even though observed data would appropriately control the type I error rate and bias.

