## 19. Appendix – SAS Code

### 19.1. Multiple Imputation

#### Imputation Model with Linear Regression and Predictive Mean Matching for sUA Imputation

The following example code will be used to perform multiple imputation to impute missing sUA for subjects with missing data due to site closure (due to COVID-19) for primary analysis:

This document is confidential.

[REDACTED]

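### Does scoring site-closure subjects on one imputed sUA value per visit, with no post-infusion values, distort the Month 6 and Month 12 response rates?

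*SAP*

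**What the plan says.** For observed subjects, SAP 9.2.1 states: "The Month 6 period will include pre-infusion and post-infusion results at Week 20, results at Week 21, pre-infusion and post-infusion results at Week 22". Week 23 and the Week 24 pre-infusion result complete the set, making seven scheduled results. The curve is built "using the available pre-infusion (or values at visit when no infusion performed) and post-infusion samples with non-missing sUA values", so a missing post-infusion sample is simply skipped.

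Imputation applies to site-closure subjects who "have < 2 visits during Month 6 with sUA available". For them, step 2 of SAP 9.2.2 fits a model that "will be fit for each sUA value comprising Month 6 (i.e., Week 20, Week 21, Week 22, Week 23, Week 24"), with only pre-infusion sUA among the sUA predictors. In step 5, "a duration of 7 days (168 hours) will be used for time between each visit", for a total of 672 hours. Neither step gives a pre-to-post interval. Appendix 19.1 introduces its program with "The following example code will be used to perform multiple imputation to impute missing sUA for subjects with missing data due to site closure", but the code itself is redacted.

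Section 9.3.1 reuses the method for Month 12 (Weeks 48, 50 and 52), the first secondary endpoint in the testing sequence, and states no between-visit interval.

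**The concern.** The same underlying sUA course could be classed differently according to whether it was observed or imputed. If an infusion brings sUA down within hours, an observed subject's Week 22 peak ends at the post-infusion sample. An imputed subject's peak declines in a straight line over the following week. One isolated high does not meet the non-responder rule ("sUA values > 6 mg/dL at 2 consecutive scheduled visits (excluding post-infusion sUA"), so nothing else settles that subject's class.

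Section 6.3.3 aims at a setting in which closures do not prevent visits. In that setting a subject still on pegloticase would have had the Week 20 and Week 22 post-infusion samples. What is at stake is a possible bias in the primary endpoint and in the first endpoint of the secondary sequence.

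**Working it through.** **The plan's own figure.** Five visits make four intervals: 4 × 168 = 672 h = 28 × 24 h, as step 5 states. If the two post-infusion values were treated as extra visits, the total would be 6 × 168 = 1008 h. So 672 h fits one value per visit. It would also fit post-infusion values placed inside the intervals, so it does not settle the reading by itself.

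**Inputs.** The 80% threshold, the 168 h spacing and linear interpolation come from the SAP and protocol. The sUA levels, the post-infusion values (0 to 5 mg/dL) and the pre-to-post gaps are assumptions, because the documents do not quantify the post-infusion fall.

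**Month 6, isolated high x at Week 22, neighbours at b.** A non-responder has more than 0.20 × 672 = 134.4 h at or above 6.

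- Five points: time at or above 6 is 336(x − 6)/(x − b). Setting this to 134.4 gives x = (6 − 0.4b)/0.6, which is 8.67 mg/dL for b = 2.
- x = 9, b = 2: 336 × 3/7 = 144 h above, 528/672 = 78.6% below. Non-responder.
- Same case with a post-infusion value 3 to 6 h later: 88.6% to 89.1%. With the pre-infusion sample drawn 48 h before infusion (288 h) and the post-infusion sample at 339 h: 86.7% to 89.8%. Responder.
- x = 7 or 8: 90.0% and 83.3% on five points, so the class does not change.

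**Other positions at Month 6.**

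| Pattern | Five points | With post-infusion values |
|---|---|---|
| Week 21 or Week 23 = 9, others 2 | 78.6% | 78.9% (post 2) to 81.2% (post 0), gap 4.5 h |
| Weeks 20 and 22 = 8, others 1 | 78.6% | 92.6% (post 1), gap 3 h |

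An isolated Week 20 high gives 168(x − 6)/(x − b) h, so it needs x > 30 − 4b = 22 mg/dL for b = 2. The direction reverses if the post-infusion value is higher than the pre-infusion one. With neighbours at 1, pre 7 and post 9, the result is 86.2%, against 91.7% on five points.

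**Month 12, assuming 336 h between visits.** Time at or above 6 for an isolated Week 50 high is 672(x − 6)/(x − b), so the limit is (6 − 0.2b)/0.8 = 7.0 for b = 2. Week 50 = 7.5 gives 672 × 1.5/5.5 = 183.3 h above, or 72.7% below. With post-infusion values (Week 48 at 0 to 2, Week 50 at 0 to 5, gaps of 3 to 51 h) it gives 83.9% to 90.0%.

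**Effect on the treatment difference.** Assume 145 randomised, split 97/48, with 71% against 43% responding. Assume also that 3 to 10 subjects are imputed 2:1 and that 5% to 20% of their responders are lost in both arms.

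- Upper case: MTX loses 0.71 × 0.20 × 6.67/97 = 0.98 points and placebo loses 0.43 × 0.20 × 3.33/48 = 0.60 points. The difference goes from 28.0 to 27.6.
- Lower case: 0.71 × 0.05 × 2/97 = 0.07 and 0.43 × 0.05 × 1/48 = 0.04 points. The difference goes to 27.97.
- Power (two-sided 0.0495, unpooled normal approximation) goes from 90.8% to 90.7% in the lower case and 90.0% in the upper.

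**The case for a change.** The strongest case for a change is that the text departs from the estimand the SAP sets itself, that the class changes sit in a plausible sUA range, and that the samples are already scheduled, so modelling them needs no new data. Month 12 is more exposed: the limit is lower (7.0 against 8.67), and the worst-case and logistic analyses are specified for Month 6 only.

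The mismatch and the arithmetic stand on the likelier reading. The call for a change does not.

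- The deciding code is redacted, so the omission is not established.
- The trigger is narrow. The headline case needs a high Week 22 with Weeks 21 and 23 low. If either neighbour also exceeds 6, the two-visit rule, read as covering imputed values, makes the subject a non-responder anyway. Predictive mean matching on earlier sUA also works against isolated spikes in a subject with low values so far.
- Month 6 is well covered. Sensitivity analysis 3 removes the site-closure subjects, analysis 4 bounds the direction that could falsely favour MTX, and the logistic supplement imputes response directly.
- Modelling post-infusion values has costs: two more variables in each of four period models, donor limits by infusion status and an assumed interval. Convergence is already a worry in step 3 ("Covariates will be removed from the model if the model is unable to converge due to quasi or complete separation"). It also opens a trap. Imputed values 2, 2, 7, 7, 2 score 65.0% on five points, in line with the two-visit rule. With post-infusion values at a 4.5 h gap they score 85.0% to 86.4%, a false response unless the rule is applied first.

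For Month 12 what remains is an unstated interval, which the visit schedule supplies (two weeks, 336 h), and the absence of a worst-case version. Section 9.3.1 does add a summary that counts missing subjects as non-responders.

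**Conclusion.** No change to the plan follows. On the likelier reading, site-closure subjects are scored on a coarser curve than fully sampled subjects, and an isolated Week 22 peak above 8.67 mg/dL (neighbours at 2) can turn a response into a non-response. That is a fair simplification for a small group. It is the same straight line that 9.2.1 gives an observed subject with no post-infusion sample, and it mostly works against showing a benefit of MTX.

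Under the assumed inputs the difference shrinks by 0.03 to 0.4 points and power by at most 0.8 points. This rests on three things the documents do not give: the number of site-closure subjects, how often isolated highs occur, and a fall in sUA after infusion. A more elaborate imputation would add assumptions and convergence risk for no material gain. How post-infusion values are handled, and the Month 12 spacing, are details an analyst can settle sensibly in the programming.
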